1.0 OBJECTIVE

In a prospective study involving 130 cardiac rehabilitation patients muscular strength will be measured with a force dynamometer (PRIMUS) on six commonly performed activities. During the first session of cardiac rehabilitation, each subject's date of birth, height, and weight will be recorded. To ensure safety, cardiovascular nurse specialists and exercise physiologists will monitor the patients for hypertension (blood pressure $>240/110$ mm Hg), arrhythmias, angina, dizziness, pain, shortness of breath, and perceived exertion. The subjects will be asked to complete a pre-activity confidence survey. On the second day of cardiac rehabilitation, a clinical exercise specialist will use the PRIMUS equipment to obtain force measurements on the six activities including: rising from a bed, rising from a chair, opening a door, lifting an object from the floor and/or placing an object overhead. Following the performance of the activities, the patients will be asked to complete a post-activity confidence survey.

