1.1 HYPOTHESIS

The purpose of this study is to determine if performed force measurements yield a different recommended weight lifted during the sternotomy healing process than the traditional gold standard of 5 pounds. A secondary endpoint data obtained will be scores from the pre and post-activity questionnaires.

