1.2 STATISTICAL METHODOLOGY

Continuous variables will be reported as means and standard deviations or medians and interquartile ranges, if skewed. Categorical variables will be reported as frequencies and per cents. To do so, patients will use the PRIMUS equipment to obtain the maximum force pounds performed during six activities. Then, their new recommended weight to lift will be 30% and 50% of that maximum. We will use a one sample t-test to determine if a difference exists between the gold standard recommendation and the force performed in the activities.

With a sample size of 130 subjects, we will have in excess of 90% power to detect a difference of 5 pounds from the gold standard recommendation, assuming a standard deviation of 5 and a type I error rate of 0.05 in a two-tailed test. With this sample size, the data will likely be normally distributed, which is a necessary assumption to perform the one sample t-test. However, if the data do not meet this assumption, we will proceed using a nonparametric alternative, the Wilcoxon Rank Sum Test.

Additionally, to examine the change in confidence after performing the 6 activities, 2 surveys will be administered: 1 prior to treatment and 1 after treatment. In the survey, subjects will be asked to rate their confidence using a 7-point Likert scale to perform selected daily tasks. Subjects' perceptions of confidence will be reported and analyzed in several ways. We will consider the changes from each of the 7 categories, the change in

percent of ‘top box’ responses, and the changes in stratified responses (positive, neutral, negative).

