4.0 STUDY PLAN

On day 1 (evaluation day), patients will report to the cardiovascular rehabilitation department. Patients will complete a medical history form and medications will be documented. The patient's case manager will review these documents with the patient, describe the cardiac rehabilitation program to the patients, and assess the patient's resting heart rate, blood pressure, height, and weight. During this evaluation session, the study will be presented to patients who meet the inclusion criteria. The nurse will conclude this session by assessing the patient for signs of edema, incision infection, and any other heart or lung problems.

On day 2 (testing day), to ensure safety, nurses and exercise physiologists will monitor the patients for hypertension, arrhythmias, angina, dizziness, pain, shortness of breath, and perceived exertion. Patients will be asked to review and sign the informed consent and a confidence survey. Thereafter, through use of a stethoscope placed above the sternum and clavicle, a cardiovascular nurse specialist will listen and document any findings of sternal clicking, moving, or grating as subject performs a repetitive chest fly routine. The PRIMUS force dynamometer will then be used to obtain one repetition maximum (1RM) strength measurements during the activities including: placing an object overhead, picking up object up from the ground, and opening a door. Once a one 1RM has been determined, the patient will then perform 5-20 repetitions at 30% and 50% 1RM of the same three exercises. Then, dynamic movements that mimic rising from a bed and rising from a chair will be performed three times by pushing against the PRIMUS force dynamometer. A post session confidence survey will be filled out by the subject. Following completion of the activities, the cardiovascular nurse specialist will listen to the sternum for changes in clicking, moving or grating. Final measurements will be assessed, including a recovery lead II ECG, heart rate, and blood pressure.

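### Does the plan leave open whether the baseline confidence survey is taken in the first session or on the testing day?

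*Combined protocol and SAP*

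**What the plan says.** Section 1.0 OBJECTIVE begins its account of the visits with intake data: "During the first session of cardiac rehabilitation, each subject's date of birth, height, and weight will be recorded". An undated sentence on safety monitoring comes next, then the survey, then the move to testing: "The subjects will be asked to complete a pre-activity confidence survey. On the second day of cardiac rehabilitation, a clinical exercise specialist", where the last sentence goes on to the force measurements. The post-activity survey closes the paragraph.

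Section 4.0 STUDY PLAN itemises the two days. On day 1 the patient gives a medical history, has resting measurements taken and hears about the study: "During this evaluation session, the study will be presented to patients who meet the inclusion criteria". No survey is listed for that day. The day 2 account opens with monitoring, "On day 2 (testing day), to ensure safety, nurses and exercise physiologists will monitor the patients for hypertension", and continues: "Patients will be asked to review and sign the informed consent and a confidence survey". The sternal check and the PRIMUS testing come after that, and then: "A post session confidence survey will be filled out by the subject".

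Section 1.1 HYPOTHESIS makes the scores an endpoint: "A secondary endpoint data obtained will be scores from the pre and post-activity questionnaires". Section 1.2 STATISTICAL METHODOLOGY gives the aim and the number of surveys but no day: "to examine the change in confidence after performing the 6 activities, 2 surveys will be administered: 1 prior to treatment and 1 after treatment".

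**The concern.** Section 1.0 has only two date markers, and the survey sentence lies between them. A reader who carries the first marker forward until the second appears will place the baseline survey in session 1. Section 4.0 places it on day 2, so the two sections seem to give different baselines for a named secondary endpoint.

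Two things would be at stake. First, the study has one group and no comparator. If the baseline were taken in session 1, any shift in confidence between sessions, over an interval the documents do not state, would be counted as change due to the activities. Second, consent is signed on day 2, so a session 1 survey would be research data collected before consent.

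**Working it through.** The plan gives no power, test or threshold for the survey, so there is no survey figure to reproduce. Its one power statement concerns the force measurements and does not depend on when the survey is taken. The check is therefore a comparison of the text.

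**Step 1: order of events.**

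| Event | Section 1.0 | Section 4.0 |
|---|---|---|
| Intake (height, weight) | first session | day 1 |
| Safety monitoring | no date | day 2 |
| Pre-activity survey | no date | day 2, with consent |
| PRIMUS testing | second day | day 2 |
| Post-activity survey | after the activities | day 2, after the activities |

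The order is the same in both columns. They differ only in where the day 2 label begins: at monitoring in 4.0, and two events later, at testing, in 1.0.

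**Step 2: does the session 1 label carry forward in 1.0?** To reach the survey it must first pass over the monitoring sentence. Section 4.0 has a closely matching sentence and dates it to day 2. The list includes perceived exertion, which presupposes effort, and 4.0 lists no exercise on day 1. So 1.0 has most likely left session 1 before it mentions the survey.

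**Step 3: count the surveys.** Section 1.2 provides for 2. Section 4.0 places 1 before testing and 1 after it, both on day 2. That leaves 2 − 2 = 0 for day 1. A session 1 survey could not be added to the schedule in 4.0; it would have to replace an explicit instruction there.

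**Step 4: fit with the aim.** Section 1.2 wants the change that follows the six activities. Its wording allows either day, but a baseline taken just before testing matches that aim more closely.

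**Step 5: size.** With the planned n = 130 (sections 1.0, 1.2 and 3.1), one patient's share of a top-box percentage is 100/130 = 0.77 percentage points. If the baseline were in session 1, each net patient who moved into the top box between sessions would add 0.77 points to that item's change. With a day 2 baseline the addition is 0. This is only the weight of one patient. The documents give no rate of movement between sessions, so no bias can be estimated from it.

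**The case for a change.** The strongest case for a change is that an endpoint should have one stated baseline time and that 1.0, taken alone, does not give it. The monitoring sentence is not conclusive either: 4.0 records resting heart rate and blood pressure on day 1, so some monitoring in session 1 is plausible. Neither 1.1 nor 1.2 names a day. With no comparator, drift between sessions could not be separated from the effect of testing, and if staff followed different sections the pooled change would mix two intervals. Dating one sentence costs almost nothing.

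Some of this stands. The sentence in 1.0 is loosely placed and, in isolation, can be misread. But the harms require staff to take a date that 1.0 does not state and set it above one that 4.0 does state, in the section written to direct conduct. No part of the document tells them to do that. The consent worry depends on the same step. Section 4.0 does not separately order signing and survey, but it names consent first and puts both in the same sitting before testing. Even on the session 1 reading, the survey would still precede the activities, so a before-and-after comparison would exist.

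**Conclusion.** This is a clerical slip in a summary paragraph, and no change to the plan is needed. Section 4.0 already fixes the baseline on day 2, at consent and before testing. An analyst working from it will compare the two day 2 surveys within each patient. An amendment would only repeat 4.0: it would alter no data collected, no analysis and no result. The primary force comparison and the sample size are unaffected on any reading.

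The conclusion assumes that staff work from the study plan section rather than inferring a schedule from the objective, and that the survey signed with consent is the pre-activity survey. The count of two surveys in 1.2 and the position of that survey before testing support the second assumption. Neither a bias nor a breach of consent is shown. If 1.0 is revised for some other reason, adding the day to that sentence would be a harmless tidy-up.

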1.1 HYPOTHESIS

The purpose of this study is to determine if performed force measurements yield a different recommended weight lifted during the sternotomy healing process than the traditional gold standard of 5 pounds. A secondary endpoint data obtained will be scores from the pre and post-activity questionnaires.

1.2 STATISTICAL METHODOLOGY

Continuous variables will be reported as means and standard deviations or medians and interquartile ranges, if skewed. Categorical variables will be reported as frequencies and per cents. To do so, patients will use the PRIMUS equipment to obtain the maximum force pounds performed during six activities. Then, their new recommended weight to lift will be 30% and 50% of that maximum. We will use a one sample t-test to determine if a difference exists between the gold standard recommendation and the force performed in the activities.

With a sample size of 130 subjects, we will have in excess of 90% power to detect a difference of 5 pounds from the gold standard recommendation, assuming a standard deviation of 5 and a type I error rate of 0.05 in a two-tailed test. With this sample size, the data will likely be normally distributed, which is a necessary assumption to perform the one sample t-test. However, if the data do not meet this assumption, we will proceed using a nonparametric alternative, the Wilcoxon Rank Sum Test.

Additionally, to examine the change in confidence after performing the 6 activities, 2 surveys will be administered: 1 prior to treatment and 1 after treatment. In the survey, subjects will be asked to rate their confidence using a 7-point Likert scale to perform selected daily tasks. Subjects' perceptions of confidence will be reported and analyzed in several ways. We will consider the changes from each of the 7 categories, the change in

percent of ‘top box’ responses, and the changes in stratified responses (positive, neutral, negative).

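### The one-sample t-test is written for the raw force performed, not for the recommended weight (30% and 50% of it) in the hypothesis, so it can point the wrong way

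*Combined protocol and SAP*

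**What the plan says.** Section 1.1 gives the study's purpose as to "determine if performed force measurements yield a different recommended weight lifted during the sternotomy healing process than the traditional gold standard of 5 pounds". Questionnaire scores are called secondary.

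Section 1.2 then takes four steps:

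- Patients use the dynamometer to "obtain the maximum force pounds performed during six activities".
- The derived quantity is defined: "their new recommended weight to lift will be 30% and 50% of that maximum".
- The one-sample t-test is to determine whether "a difference exists between the gold standard recommendation and the force performed in the activities".
- With 130 patients, power above 90% is claimed to "detect a difference of 5 pounds from the gold standard recommendation, assuming a standard deviation of 5", at a two-sided type I error rate of 0.05.

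Section 4.0 describes a one-repetition maximum, followed by work at 30% and 50% of it, for three activities: overhead placement, lifting from the ground and opening a door. The bed and chair movements are performed three times against the dynamometer, with no 30% or 50% step.

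**The concern.** The hypothesis concerns the recommended weight, but the test sentence names the force performed, which echoes the wording used for the measured maximum. No section applies the t-test to the 30% or 50% values, so the quantity that answers Section 1.1 is defined and then left out of the analysis.

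A maximum must be at least as large as any fraction of itself. Comparing the maximum with 5 lb therefore favours a finding above 5 lb, whatever the derived recommendation shows. The result could be read as support for a weight above 5 lb when both of the plan's own recommended weights are below it. Section 2.0 calls the consequences of sternal complications potentially grave and expects the force data to inform exercise prescriptions, so the direction of the error matters.

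The power statement does not settle the matter, because it does not say whether the 5 lb difference and the SD of 5 refer to raw force or to recommended weight.

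**Working it through.** **Inputs from Sections 1.1 and 1.2:** n = 130; reference value 5 lb; fractions 0.30 and 0.50; planned difference 5 lb; SD 5; two-sided alpha 0.05.

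**Assumed:** the mean maximum force, which the documents do not give and which is shown below as a range. The SD of 5 is first taken as the SD of maximum force.

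**1. The plan's own power figure.** The noncentrality is (5/5) × √130 = 11.40 on 129 degrees of freedom. Power exceeds 99.9%, consistent with the stated figure above 90%; 13 patients would already give 91%. The power figure is not the fault.

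**2. Where the two questions part.** For maximum X, 0.50X > 5 requires X > 5/0.50 = 10 lb, and 0.30X > 5 requires X > 5/0.30 = 16.7 lb.

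**3. The written test.** SE = 5/√130 = 0.4385 lb. The test declares force above 5 lb once the observed mean exceeds 5 + 1.9785 × 0.4385 = 5.87 lb.

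**4. The same patients on each scale.** For fraction f and mean maximum μ, t = (fμ − 5)/(f × 5/√130). The standard errors are 0.4385 (f = 1), 0.2193 (f = 0.50) and 0.1316 (f = 0.30).

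| Mean maximum (lb) | Raw force: t | 50% weight (lb): t | 30% weight (lb): t |
|---|---|---|---|
| 5 | 0.00 | 2.5: −11.40 | 1.5: −26.60 |
| 8 | +6.84 | 4.0: −4.56 | 2.4: −19.76 |
| 10 | +11.40 | 5.0: 0.00 | 3.0: −15.20 |
| 15 | +22.80 | 7.5: +11.40 | 4.5: −3.80 |
| 20 | +34.21 | 10.0: +22.80 | 6.0: +7.60 |

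- At 8 lb the raw test is significant above 5 lb with probability over 99.9%. The 50% weight is significantly below with probability 99.5%, and the 30% weight with probability over 99.9%.
- At 15 lb the 30% weight is significantly below 5 lb with probability 96.5%, while the raw test says above.
- At 5 lb the raw test rejects only 5% of the time although both recommended weights are far from 5 lb, so the mismatch can also hide a difference.
- Near the upper limits the recommended-weight test is merely non-significant: from 10 − 0.87 = 9.1 lb (50%) and 16.7 − 0.87 = 15.8 lb (30%).

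**5. A larger SD.** With a raw SD of 10 and a mean maximum of 7.5 lb, the raw test finds force above 5 lb with power 81%. The 50% weight (3.75 lb) is found below 5 lb with the same power.

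**6. The scale of the power statement.**

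- On the force scale, the planned upward alternative is a mean maximum of 5 + 5 = 10 lb. The 50% weight is then exactly 5.0 lb and the 30% weight 3.0 lb.
- On the recommended-weight scale, it is a recommendation of 10 lb, so a mean maximum of 10/0.50 = 20 lb or 10/0.30 = 33.3 lb. There is then no reversal.
- The two stated figures cannot describe both fractions. If 0.50X has mean 10 and SD 5, then X has mean 20 and SD 10, and 0.30X has mean 6 and SD 3.

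**7. Detectable differences at 90% power, n = 130.** With an SD of 5 on the tested variable, 1.43 lb. If the SD of 5 belongs to maximum force, the recommended-weight SDs are 2.5 and 1.5 lb, and the detectable differences are 1.43 × 0.50 = 0.72 lb and 1.43 × 0.30 = 0.43 lb.

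**The case against.** The strongest reply is that the wording is loose rather than the test wrong. The sentence just before the t-test defines the recommended weight, the hypothesis is stated in those terms, and in Section 4.0 patients do perform repetitions at 30% and 50% of maximum. The force performed might mean those loads. That reading is possible, but no section states it, and Section 4.0 supports it for three activities only. An analyst following the sentence literally would test the maximum.

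The reversal also depends on assumed means, and this stands. No expected force is given, and a mean of 8 lb with an SD of 5 would imply about 5% negative forces under normality (Φ(−1.6) = 0.055), so it is an illustration and not a forecast. Above 16.7 lb only the size of the difference is overstated.

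Strictly, a raw-force test would report correctly that maximum force exceeds 5 lb; the error comes when that result is used to answer Section 1.1. But this is the only test the plan gives for Section 1.1. Descriptive summaries might expose the discrepancy, but the plan does not say the derived weights will be summarised.

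The documents do not call this test primary. That status is inferred from the questionnaires being called secondary.

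**Conclusion.** The concern holds. As written, the test variable is the unscaled force, and the test does not answer the question in Section 1.1. If the true mean maximum lies between 5 and 10 lb, both recommended weights are below 5 lb while raw force is above it; between 10 and 16.7 lb this is true of the 30% weight alone. With an SD of 5 and 130 patients, the written test becomes significant from an observed mean of 5.87 lb, so most of that range would yield a significant result in the opposite direction to at least one recommendation. Above 16.7 lb the direction is right and the difference is too large.

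The 10 and 16.7 lb limits follow from the plan's fractions alone. The t-values and probabilities rest on the assumed means and on reading the SD of 5 as that of maximum force. The stated power is arithmetically sound, but it is attached to an unnamed variable.

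**What to change.** Replace the test sentence in Section 1.2 with: *One-sample t-tests will compare each patient's recommended weight (0.30 × maximum and 0.50 × maximum for that activity) with 5 lb.* This is identical to testing the maximum against 16.7 lb and 10 lb. Any nonparametric fallback should use the same variables.

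Then:

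- State whether the 5 lb difference and the SD of 5 refer to maximum force or to recommended weight, and restate the power on the tested scale.
- Name the activities tested, since Section 4.0 gives a one-repetition maximum for only three.
- State which fraction and activity carry the main conclusion, or how multiplicity is handled. Two fractions give 2 × 3 = 6 tests for three activities and 2 × 6 = 12 for six.

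The cost is wording and a few analysis decisions, with no new data. If the 5 lb difference and SD of 5 apply to the recommended weight, the power of each test at 0.05 remains above 99.9%, so 130 patients need not change on that account. The results will look less striking than a raw-force comparison.

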Many patients are referred to cardiac rehabilitation programs following sternotomy. Cardiac rehabilitation is a program of supervised exercise and risk factor education prescribed by the patient’s physician. Traditionally, the exercise prescription comprises aerobic activities such as walking and cycling, which utilize large muscle groups in rhythmic contractions and improve exercise tolerance and functional capacity. However, according to common goals that patients claim, they are more interested in being able to return to activities of daily living such as the following: rising from a bed, rising from a chair, opening a door, lifting objects from the floor and/or placing objects overhead. These movements are reflected in a new philosophy (Keep Your Move in the Tube™) for replacement of traditional sternal precautions. The Baylor Institute for Rehabilitation and the post-sternotomy surgical unit on 13 Roberts have adopted and currently using the Keep Your Move in the Tube philosophy.

Use of the PRIMUS will enable us to document the force pounds that patients can actually lift. If this information was available to cardiac rehabilitation clinicians, specific exercise prescriptions could be made to help patients reach their goals and gain confidence after a cardiac event.

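### Section 1.2 tests force against 5 lb, but the hypothesis in 1.1 is about the recommended weight, which is 30% or 50% of that force

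*Combined protocol and SAP*

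**What the plan says.** **Hypothesis.** Section 1.1 gives the purpose: to "determine if performed force measurements yield a different recommended weight lifted during the sternotomy healing process than the traditional gold standard of 5 pounds".

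**Recommended weight.** Section 1.2 takes each patient's maximum force and says that "their new recommended weight to lift will be 30% and 50% of that maximum". That is two values per maximum.

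**Test.** Section 1.2 then announces "a one sample t-test to determine if a difference exists between the gold standard recommendation and the force performed in the activities". The quantity set against 5 lb in that sentence is force, not either recommended weight.

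**Power.** "With a sample size of 130 subjects, we will have in excess of 90% power to detect a difference of 5 pounds" from the reference, "assuming a standard deviation of 5 and a type I error rate of 0.05 in a two-tailed test". The text does not say whether the difference and the SD are on the scale of the force, the 50% weight or the 30% weight.

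**Activities.** Section 1.0 speaks of "force measurements on the six activities including: rising from a bed, rising from a chair, opening a door, lifting an object from the floor" and adds overhead placement, so six are announced and five named. Section 4.0 describes a one-repetition maximum for three (overhead, floor and door), after which "the patient will then perform 5-20 repetitions at 30% and 50% 1RM of the same three exercises". Bed and chair rising are pushed three times against the device, with no one-repetition maximum described. No section says whether the test is run per activity, on a per-patient average, or on one named activity.

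**The concern.** The test as worded and the hypothesis concern different quantities. A result for force does not carry over to a recommended weight that is a fixed fraction of it, because the 5 lb reference is not scaled by the same fraction. The test could therefore declare a difference from 5 lb that says nothing about the recommended weight, or that points the other way.

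The study is meant to inform advice on lifting, so direction matters as much as significance. A force above 5 lb could be read as showing that the 5 lb limit is too low, when the weights derived from that force by the plan's own rule lie below 5 lb.

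The open number of activities adds a smaller issue. If each activity is tested and claimed separately, the single 0.05 does not cover the set of claims.

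**Working it through.** **1. The plan's own figure.** Inputs from 1.2: n = 130, difference 5 lb, SD 5, two-sided 0.05. Noncentrality = (5/5) × √130 = 11.40 on 129 degrees of freedom. Power from the noncentral t exceeds 99.9%, and 90% power would need only 13 subjects. The claim of more than 90% is true for any single variable with these inputs.

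**2. What equality with 5 lb means for each candidate variable.** Let M be the mean maximum.
- Force: M = 5 lb.
- 50% weight: 0.5M = 5, so M = 10 lb.
- 30% weight: 0.3M = 5, so M = 5/0.3 = 16.7 lb.

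The documents give no expected M, so the rows below are illustrations.

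| M (lb) | Force vs 5 | 50% weight | 30% weight |
|---|---|---|---|
| 5 | equal | 2.5, below | 1.5, below |
| 8 | above | 4.0, below | 2.4, below |
| 10 | above | 5.0, equal | 3.0, below |
| 13 | above | 6.5, above | 3.9, below |
| 20 | above | 10.0, above | 6.0, above |

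The row for 10 lb is instructive. If the 5 lb difference is on the force scale and upward, the study is powered for M = 5 + 5 = 10 lb, which is exactly the null for the 50% weight.

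**3. The same data through the test.** Take M = 8 lb and assume that the SD of 5 belongs to force. The expected t-statistics are about:
- Force: (8 − 5)/5 × 11.40 = 6.84
- 50% weight (SD 0.5 × 5 = 2.5): (4.0 − 5)/2.5 × 11.40 = −4.56
- 30% weight (SD 0.3 × 5 = 1.5): (2.4 − 5)/1.5 × 11.40 = −19.8

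All three are clearly significant, and force has the opposite sign to both weights.

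**4. The SD.** One SD of 5 can describe only one of the three variables.
- If it is the SD of the 50% weight, the maximum has SD 5/0.5 = 10 lb and the 30% weight has SD 0.3 × 10 = 3 lb.
- If it is the SD of the 30% weight, the maximum has SD 5/0.3 = 16.7 lb and the 50% weight has SD 0.5 × 16.7 = 8.3 lb.

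**5. Activities.** If k activities are tested separately at 0.05, all nulls are true and the tests are independent, the chance of at least one false claim is 1 − 0.95^k: 14.3% (k = 3), 22.6% (k = 5), 26.5% (k = 6). Correlation lowers it. Simulation with n = 130 gives 12.3% (k = 3) and 20.8% (k = 6) at an assumed correlation of 0.5, and about 8% and 11% at 0.9. The documents give no correlation. Testing both percentages does not raise the error within an activity, because 0.3M and 0.5M cannot both equal 5, so at most one of the two nulls is true.

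**6. Cost of Holm.** Difference detectable with 90% power at n = 130 and SD 5, noncentral t, at the strictest Holm step:

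| Level | Detectable difference (lb) |
|---|---|
| 0.05 (one test) | 1.43 |
| 0.05/3 | 1.63 |
| 0.05/5 | 1.71 |
| 0.05/6 | 1.74 |

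Power at 5 lb stays essentially 100%. At an assumed SD of 15, it falls from 96.5% to 91.4% (k = 3), 88.0% (k = 5) or 86.7% (k = 6).

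**The case against.** The strongest reply is that the force wording is shorthand. The test sentence follows directly on the definition of the recommended weight, and 1.1 states the purpose plainly, so an analyst would probably test the recommended weight. That is plausible, and it makes this a fault of wording rather than of design. But the sentence still names force, and even the charitable reading leaves two percentages and an unassigned SD.

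It is also fair to say that the question is only whether the weight differs from 5 lb. For M strictly between 10 and 16.7 lb both weights do differ. A reader might infer that the choice of percentage reverses the answer. In that range it reverses the direction, not the answer to the question as put, and no figure in the documents places M there.

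A reader might also infer that, with two percentages available, the comparison cannot fail. That is a fact about population means, not about test results. If the maximum has mean 13.3 lb and an assumed SD of 30 lb, neither test rejects in about 52% of trials. Only with a much smaller SD, such as the 10 or 16.7 lb in step 4, is a double non-rejection practically excluded.

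On multiplicity, the reply largely succeeds. The plan states no rule that any one activity suffices, and Background 2.0 says only that "specific exercise prescriptions could be made to help patients reach their goals and gain confidence after a cardiac event", which hints at activity-level use without committing the analysis to it. With a true 5 lb difference and SD 5 in every activity, Holm and unadjusted conclusions agreed in all 20,000 simulated trials in each scenario (k = 3 or 6, correlation 0 or 0.5). Nor is k settled: the activity lists in 1.0 and 4.0 are worded as non-exhaustive, and force may exist for five activities.

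**Conclusion.** The point stands as a mismatch between the test and the hypothesis. As written, 1.2 can declare a difference from 5 lb that does not concern the recommended weight. The three nulls sit at mean maxima of 5, 10 and 16.7 lb. This follows from the plan's two percentages and its 5 lb reference, and needs no assumption about the distribution. Whether it affects this trial's conclusion depends on where the mean maximum falls, which the documents do not say.

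The stated power is correct and unaffected. A reader might infer an actual type I error of 14.3% to 26.5%. The documents do not support that as a description of the plan: it is a worst case that needs separate tests, every null true, independence and a claim resting on any one activity.

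The wording should be corrected before analysis, so that the tested variable is not chosen after the data are seen.

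**What to change.** In Section 1.2:

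1. Make the recommended weight the tested variable, to match 1.1.
2. Run and report the comparison with 5 lb separately for the 30% and the 50% weight, each with a confidence interval and the direction, so that every claim names its percentage. Naming one percentage as primary is optional and the sponsor's choice.
3. State in the power sentence that the SD of 5 refers to the recommended weight, and at which percentage.
4. Reconcile the number of activities across 1.0, 1.2 and 4.0 (six stated, five named, three with a one-repetition maximum).
5. State the level of the claim. For activity-level claims, apply Holm across the k activities at an overall two-sided 0.05. For one overall claim, test each patient's average over the activities, or one named activity, at 0.05 without adjustment.

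The cost is wording, with no change to the 130 subjects. If Holm is used, restate the power sentence with the detectable difference for the chosen k. A single overall test costs no alpha, but a per-patient average can hide activities that lie on either side of 5 lb. None of this takes a position on which percentage or lifting limit is clinically right.
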